- i. The patient has a past or current history of cancer or malignant tumor in the past 5 years, except for appropriately treated non-melanoma skin carcinoma.
- j. The patient is pregnant or lactating.
- k. The patient has a history of hypersensitivity reactions to injected proteins, including monoclonal antibodies.
- l. The patient has participated in a clinical study of a new chemical entity or a prescription medicine within 2 months or 5 half-lives before administration of the first dose of the IMP, whichever is longer.
- m. The patient has participated in a clinical study of a monoclonal antibody within 3 months or 5 half-lives before administration of the first dose of the IMP, whichever is longer, unless it is known that the patient received placebo during the study.
- n. The patient has a history of prior exposure to a monoclonal antibody targeting the CGRP pathway (AMG 334, ALD304, LY2951742, or fremanezumab). If patient has participated in a clinical study with any of these monoclonal antibodies, it has to be confirmed that the patient received placebo in order to be eligible for this study.
- o. The patient has any finding in the baseline 12-lead ECG considered clinically significant in the judgment of the investigator.
- p. The patient has any finding that, in the judgment of the investigator, is a clinically significant abnormality, including serum chemistry, hematology, coagulation, and urinalysis test values (abnormal tests may be repeated for confirmation).
- q. The patient has hepatic enzymes (alanine aminotransferase and aspartate aminotransferase) $>1.5 \times$ the upper limit of normal (ULN) range after confirmation in a repeat test, or the patient has suspected hepatocellular damage that fulfills criteria for Hy's law at screening.
- r. The patient has serum creatinine $>1.5 \times$ the ULN or evidence of clinically significant renal disease in the judgement of the investigator.
- s. The patient cannot participate or successfully complete the study, in the opinion of their healthcare provider or the investigator, for any of the following reasons:
 - mentally or legally incapacitated or unable to give consent for any reason
 - in custody due to an administrative or a legal decision, under tutelage, or being admitted to a sanitarium or social institution
 - unable to be contacted in case of emergency

- has any other condition, which, in the opinion of the investigator, makes the patient inappropriate for inclusion in the study

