4. SELECTION AND WITHDRAWAL OF PATIENTS

Prospective waivers (exceptions) from study inclusion and exclusion criteria to allow patients to be randomized/enrolled are not granted by the sponsor ([Appendix C](#)). Any deviation from the eligibility criteria will result in study drug discontinuation in the event that a patient has not been dosed.

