- n. The patient has a history of prior exposure to a monoclonal antibody targeting the CGRP pathway (AMG 334, ALD304, LY2951742, or fremanezumab). If patient has participated in a clinical study with any of these monoclonal antibodies, it has to be confirmed that the patient received placebo in order to be eligible for this study.
- o. The patient has any finding in the baseline 12-lead ECG considered clinically significant in the judgment of the investigator.
- p. The patient has any finding that, in the judgment of the investigator, is a clinically significant abnormality, including serum chemistry, hematology, coagulation, and urinalysis test values (abnormal tests may be repeated for confirmation).
- q. The patient has hepatic enzymes (ALT and AST) $>1.5 \times$ the upper limit of normal (ULN) range after confirmation in a repeat test, or the patient has suspected hepatocellular damage that fulfills criteria for Hy's law at screening.
- r. The patient has serum creatinine $>1.5 \times$ the ULN or evidence of clinically significant renal disease in the judgement of the investigator.
- s. The patient cannot participate or successfully complete the study, in the opinion of their healthcare provider or the investigator, for any of the following reasons:
 - mentally or legally incapacitated or unable to give consent for any reason
 - in custody due to an administrative or a legal decision, under tutelage, or being admitted to a sanitarium or social institution
 - unable to be contacted in case of emergency
 - has any other condition, which, in the opinion of the investigator, makes the patient inappropriate for inclusion in the study
- t. The patient is an employee of the sponsor/participating study center who is directly involved in the study or is the relative of such an employee.

- u. The patient has an active implant for neurostimulation used in the treatment of CH.
- v. The patient is a member of a vulnerable population (eg, people kept in detention).
- w. The patient has a history of alcohol and/or drug abuse that in the investigator’s opinion could interfere with the study evaluations or the patient’s safety.

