APPENDIX J. GUIDANCE ON SAFETY MONITORING

Guidance on Monitoring Patients with Elevated Liver Function Tests

Liver enzymes (ALT, AST, GGT, and ALP) as well as total, direct, and indirect bilirubin will be measured at each study visit.

In any case of elevated ALT or AST to a level exceeding $\geq 2 \times$ the ULN (including patients whose baseline ALT or AST levels are $\geq 2 \times$ and $\leq 3 \times$ the ULN, who may be enrolled in the study), a thorough medical history and physical examination with a focus on liver disease should be undertaken.² In addition, the patient should be instructed to refrain from alcoholic beverages.

In case of symptoms compatible with drug-induced liver injury during the study, patients will be instructed to return to the study center for an unscheduled visit or to go to the emergency room to measure liver enzymes as soon as possible. Solitary elevations of total, direct, or indirect bilirubin, not accompanied by elevations of ALT or AST should be managed according to the discretion of the treating physician.

Elevation of Either ALT or AST to $\geq 3 \times$ ULN

Confirmation is required prior to IMP discontinuation in cases of elevation of either ALT or AST $\geq 3 \times$ ULN. (Note: In cases of elevation of ALT or AST $\geq 8 \times$ the ULN, no confirmation is required prior to IMP discontinuation, but the assessments below should be performed.) The following procedures should be followed:

- The day in which the abnormal value is received from the laboratory will be considered as day 0.
- The investigator should repeat the test for confirmation purposes (this may be performed in a local laboratory along with complete blood cell [CBC] count and differential to assess for eosinophilia; in general, in case a blood sample is sent to a local laboratory, the following assessments [and reference ranges] are mandatory: ALT [serum glutamic pyruvic transaminase], AST [serum glutamic oxaloacetic transaminase], ALP, bilirubin [total, direct, and indirect], CBC [with differential for eosinophil count, separate tube], and INR [separate tube; not to be sent in a confirmatory test]). The investigator should also question the patient regarding symptoms.

The abnormality will be regarded as confirmed in each of the following scenarios:

- the baseline value was within the normal range and ALT or AST is still $\geq 3 \times$ the ULN
- the baseline value was above the ULN and ALT or AST is $\geq 2 \times$ the baseline value

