² Thorough medical history with a focus on liver disease: personal or family history of liver disease; personal history of a systemic disease with potential liver involvement; exposure to alcohol, medications (prescription or over-the-counter), herbal preparations, dietary supplements, recreational drugs, special diets, or environmental chemical agents; potential exposure to infectious agents (eg, travel to developing countries, history of potential exposure to blood or blood products, high-risk sexual relations); and any additional information deemed relevant by the investigator. Physical examination, including signs of chronic liver disease.

Additional Tests/Evaluations:

Upon confirmation of the abnormality as noted above, the following additional evaluations should be performed and results should be recorded in the CRF:

- serology for hepatitis A (antibody and immunoglobulins M and G), B (core antibody total, core immunoglobulin M, and surface antigen), and C viruses (central laboratory)
- serology for autoimmune hepatitis: anti-nuclear antibodies (titer), anti-smooth muscle antibodies, and anti-liver kidney microsomal antibodies (central laboratory); further testing may be required in case of a positive result for hepatitis B or C
- ultrasound examination of the liver and biliary tract at the investigator's discretion
- other diagnostic tests/consultations as deemed necessary by the investigator (eg, serology for hepatitis E virus in case of travel to endemic geography)
- observation and follow-up (to be performed after the abnormality was confirmed as above)

ALT or AST $\geq 3 \times$ ($>3.5 \times$ the ULN if the Baseline Value is $>2.5 \times$ the ULN) but $<5 \times$ the ULN

In addition to the above procedures required for any elevation to levels $>3 \times$ the ULN:

- Alanine aminotransferase, AST, GGT, ALP, total bilirubin, direct bilirubin, indirect bilirubin, CBC and differential (to assess for eosinophilia), and INR should be monitored on days 5 (± 2 days), 8 (± 2 days), 14 (± 3 days), and 28 (± 3 days). On at least 1 of these days, the test should be performed centrally. (The INR should be sent to a local laboratory only.)
- In cases where a local laboratory is used, the results should be recorded in the CRF, accompanied by the reference range of the relevant measurements.

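### Appendix J allows enrolment at baseline ALT or AST of 2–3× ULN, exclusion q stops at 1.5× ULN, and Appendix J's confirmation rule does not fit its own tier for baselines above 2.5× ULN

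*Protocol*

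**What the plan says.** **Entry.** Exclusion q in Protocol Section 4.2 reads: "The patient has hepatic enzymes (ALT and AST) $>1.5 \times$ the upper limit of normal (ULN) range after confirmation in a repeat test". The synopsis has the same limit: "The patient has hepatic enzymes (alanine aminotransferase and aspartate aminotransferase) $>1.5 \times$ the upper limit of normal (ULN) range". Section 4 adds: "Prospective waivers (exceptions) from study inclusion and exclusion criteria to allow patients to be randomized/enrolled are not granted by the sponsor". Appendix J, in its paragraph on ALT or AST reaching 2× ULN, includes patients whose baseline "levels are $\geq 2 \times$ and $\leq 3 \times$ the ULN, who may be enrolled in the study".

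**Confirmation.** Appendix J says: "Confirmation is required prior to IMP discontinuation in cases of elevation of either ALT or AST" at or above 3× ULN; from 8× ULN upward no confirmation is needed. With a normal baseline, the elevation is confirmed if the repeat is still at least 3× ULN. With a raised baseline, the condition is: "the baseline value was above the ULN and ALT or AST is $\geq 2 \times$ the baseline value".

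**After confirmation.** The additional evaluations (viral and autoimmune hepatitis serology among them) follow confirmation, and their list ends with "observation and follow-up (to be performed after the abnormality was confirmed as above". The lowest monitoring tier is 3× to <5× ULN, with its lower bound moved to >3.5× "the ULN if the Baseline Value is $>2.5 \times$ the ULN". The last bullet of that tier deals with persistence and, for a raised baseline, uses 2× ULN rather than twice baseline.

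**The concern.** Two instructions to sites point in opposite directions on who may enter. Section 4.2 sets eligibility, but Sections 3.4 and 4.3 send investigators to Appendix J for the hepatic discontinuation criteria, so sites will read and use it. A site that relies on its enrolment remark creates an eligibility deviation. Protocol Appendix C lists that as a possible important deviation, and SAP Section 3.4 removes such a patient from the per-protocol set.

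The wording differs as well as the limit. Exclusion q joins the two enzymes with *and*; Appendix J uses *or*. Read literally, q lets through a patient with only one enzyme raised.

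In patients who do enter with a raised baseline, some repeat values at or above 3× ULN would not count as confirmed. The additional evaluations and scheduled follow-up would then not be triggered, and the requirement to confirm before stopping IMP below 8× ULN would be unmet. The study has no Data Monitoring Committee (Section 5.9.3), so the site-level liver rules should be unambiguous.

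**Working it through.** All values are multiples of ULN; *b* is baseline ALT or AST.

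**Inputs**
- Exclusion limit: >1.5 (Section 4.2 q and synopsis).
- Enrolment range in Appendix J: 2 to 3.
- Confirmation when *b* > 1: repeat value ≥ 2*b* (Appendix J).
- Lowest tier: 3 to <5, or >3.5 to <5 if *b* > 2.5 (Appendix J).
- Persistence level when *b* > 1: 2 (Appendix J).

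**Step 1, entry.** The range that q allows (≤1.5) and the range 2 to 3 have no value in common. The *and* wording does not rescue this: a patient with both enzymes confirmed at 2–3 is excluded by q on either reading.

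**Step 2, confirmation threshold.** Threshold = 2*b*. Repeat values from 3 up to 2*b* are elevated but unconfirmed.

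| Baseline *b* | Confirms at (2*b*) | Repeat values ≥3 left unconfirmed | Part of the lowest tier that can confirm |
|---|---|---|---|
| 1.5 | 3.0 | none | 3.0 to <5 |
| 2.0 | 4.0 | 3.0 to <4.0 | 4.0 to <5 |
| 2.5 | 5.0 | 3.0 to <5.0 | none |
| 2.6 | 5.2 | 3.0 to <5.2 | none |
| 3.0 | 6.0 | 3.0 to <6.0 | none |

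For 1 < *b* ≤ 1.5, 2*b* ≤ 3.0, so every repeat value of 3 or more confirms and the rule works.

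**Step 3, the tier for *b* > 2.5.** Here 2*b* > 5.0. The tier is >3.5 to <5, so no repeat value can both confirm and lie inside it.

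**Step 4, persistence.** The level is 2× ULN. Any patient with *b* between 2 and 3 already meets it at baseline, whereas confirmation for the same patient needs 4 to 6.

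**Step 5, how a baseline above 1.5 could arise.** There are three routes: a site follows the Appendix J remark; only one enzyme is raised; or the predose visit 2 sample serves as baseline. Protocol Table 2 labels visit 2 as baseline. SAP Section 8.8 takes the last value before first dose, although that definition is for the laboratory summaries and Appendix J does not define baseline itself.

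**The case against.** The strongest reply is that the governing rule is clear. Section 4.2 and the synopsis agree, waivers are barred, and Appendix C says an eligibility deviation in an undosed patient always leads to study drug discontinuation. The conflicting words are a parenthesis in a guidance appendix. For patients plainly within q the confirmation rule works and the >2.5× branch never applies. This limits the reach of the second part, but it does not remove the contradiction: the parenthesis is current text and reads as permission.

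Secondly, Appendix J does not say whether the first or the repeat value assigns the tier. With baseline 2.6, a first value of 4.8 lies in the tier and a repeat of 5.2 confirms. A confirmed value could also fall back into the tier later. Both readings are possible, so the branch is not unreachable on every reading. Neither is written down, and neither helps a patient whose first and repeat values both stay between 3.5 and 5.

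Thirdly, the effect on stopping IMP is narrow. No stopping rule applies to an isolated, asymptomatic value of 3 to <5, so lack of confirmation withholds nothing there. The rules combining ≥3× with INR, bilirubin or symptoms call for immediate discontinuation. An unconfirmed value of 5 or more needs a baseline above 2.5. This stands. What is lost in most of the unconfirmed band is the additional evaluations and scheduled follow-up.

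Finally, other safeguards do not depend on confirmation: history and examination at 2× ULN, a repeat test with symptom questioning at 3×, special-interest reporting at 3× (Section 7.1.7), and liver enzymes at every visit. These reduce the clinical consequence but do not resolve the wording.

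**Conclusion.** The concern holds in both parts. The protocol states two incompatible entry ranges, at most 1.5× ULN and 2–3× ULN. Within Appendix J, a confirming repeat value for a baseline above 2.5× ULN always exceeds 5× ULN and so lies above the tier set for that baseline. The unconfirmed band is nil up to a baseline of 1.5× ULN, then widens to 1.0, 2.0 and 3.0 multiples of ULN at baselines of 2.0, 2.5 and 3.0.

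The statement about the tier takes the repeat value as the one to be placed in it, which Appendix J leaves open. The number of patients concerned cannot be derived from the documents. There is no effect on sample size, power or alpha. It should be fixed because it bears on eligibility and liver-safety monitoring.

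**What to change.** Reconcile exclusion q, in Section 4.2 and the synopsis, with the enrolment remark in Appendix J, and settle whether the criterion concerns both enzymes or either one. Within Appendix J, reconcile the confirmation rule for raised baselines, the tier for baselines above 2.5× ULN and the persistence wording of that tier. State which value counts as baseline and whether the first or the repeat value assigns the tier. Which limits apply is for the sponsor's medical team; none is proposed here.

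The cost is protocol wording at the next amendment and a note to sites. No new procedure is needed and no analysis changes.

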- Should the abnormality ($\geq 3 \times$ the ULN in case baseline was within the normal range or $\geq 2 \times$ the ULN in case the baseline value was above ULN but still $<5 \times$ the ULN) persist further, the patient will be followed according to the investigator's discretion, but a blood sample for ALT, AST, GGT, ALP, and total bilirubin, direct bilirubin, indirect bilirubin should be sent to the central laboratory at least once a month.

ALT or AST $\geq 5 \times$ but $<8 \times$ the ULN

In addition to the above procedures required for any elevation to levels $>3 \times$ the ULN:

- Alanine aminotransferase, AST, GGT, ALP, total bilirubin, direct bilirubin, indirect bilirubin, CBC and differential count (to assess for eosinophilia), and INR should be monitored twice a week.
- At least for every other measurement, the tests should be sent to the central laboratory. The rest of the tests may be sent to a local laboratory. The INR should always be sent to a local laboratory.

ALT or AST $\geq 8 \times$ the ULN

In addition to the above procedures required for any elevation to levels $>3 \times$ the ULN:

- The IMP should be discontinued immediately, and the early withdrawal visit should be performed.
- For follow-up guidance, please see below section “Follow-Up of Liver Enzymes after Stopping Rules Are Met.”

Stopping Rules

In the following circumstances, the IMP will be discontinued immediately:

- any increase in ALT or AST to $\geq 3 \times$ the ULN, combined with INR $>1.5 \times$ the ULN or total bilirubin $>2 \times$ the ULN
- any increase in ALT or AST to $\geq 3 \times$ the ULN, which is accompanied by symptoms clearly associated with impaired liver function (eg, vomiting, nausea, fever, rash, and eosinophilia) and not deemed related to other diseases (eg, vomiting or nausea triggered by cluster headache)
- any increase in ALT or AST to levels ≥ 5 but $<8 \times$ the ULN, which is persistent for ≥ 2 weeks of repeated measurements
- any increase in ALT or AST to levels $\geq 8 \times$ the ULN
- in any case where monitoring of liver enzymes cannot be performed according to the protocol guidance

Follow-Up of Liver Enzymes After Stopping Rules Are Met

- A patient who meets the above criteria for discontinuation of the IMP should be invited to the investigational site to return the IMP. Early withdrawal visit activities should be performed as soon as possible.

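### Appendix J is inconsistent on stopping IMP at ALT or AST 3× to <8× ULN: one rule requires a confirmatory test first, while two Stopping Rules require an immediate stop

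*Protocol*

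**What the plan says.** **Confirmation text (Appendix J, elevation of either enzyme to ≥3× ULN).** It states: "Confirmation is required prior to IMP discontinuation in cases of elevation of either ALT or AST" to that level. A note makes one exception, at ≥8× ULN: "no confirmation is required prior to IMP discontinuation, but the assessments below should be performed".

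Confirmation means a repeat laboratory test. For a normal baseline, the finding is confirmed if "the baseline value was within the normal range and ALT or AST is still" ≥3× ULN. For a raised baseline, the repeat must be at least twice the baseline value. A repeat at a local laboratory must include bilirubin, and the patient is to be asked about symptoms, but neither enters the definition of confirmation. INR is described as "separate tube; not to be sent in a confirmatory test".

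The next steps depend on the result: "Upon confirmation of the abnormality as noted above, the following additional evaluations should be performed". That list ends with "observation and follow-up (to be performed after the abnormality was confirmed as above".

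**Stopping Rules (later in Appendix J).** They begin: "In the following circumstances, the IMP will be discontinued immediately". Five circumstances follow:

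1. any rise to ≥3× "the ULN, combined with INR" above 1.5× ULN or total bilirubin above 2× ULN;
2. any rise to ≥3× ULN with symptoms that clearly point to impaired liver function and are not put down to another disease, such as nausea from a cluster attack;
3. 5× to <8× ULN persisting over at least 2 weeks of repeat tests;
4. ≥8× ULN;
5. liver enzymes cannot be monitored as the protocol asks.

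Once a rule is met, an early withdrawal visit follows, then at least 30 days of follow-up with liver enzymes at least weekly.

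**The concern.** The first two Stopping Rules describe the patients who matter most for liver safety. The bilirubin limb of the first rule closely tracks the enzyme and bilirubin thresholds in the protocol's Hy's law definition (Section 7.1.5.1). For these patients, at 3× to <8× ULN, one part of Appendix J says to wait for a repeat and another says to stop now. Two sites could follow the protocol faithfully, see the same values and decide differently.

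The written rule carries weight here. Liver enzyme elevation is a listed potential risk (Section 1.3.1). Sections 3.4 and 4.3 send investigators to Appendix J for the hepatic discontinuation criteria. About 80 centers are planned (Section 3.2), and there is no Data Monitoring Committee (Section 5.9.3).

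**Working it through.** The plan states no figure on this point, so the check sets the texts side by side and then bounds the size.

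**1. Each Stopping Rule against the confirmation text**

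| Rule | Trigger | Against the confirmation text |
|---|---|---|
| 1 | ≥3× ULN plus INR or bilirubin | Conflict at 3× to <8× |
| 2 | ≥3× ULN plus liver symptoms | Conflict at 3× to <8× |
| 3 | 5× to <8×, persistent on repeats | None: repeats are built in |
| 4 | ≥8× ULN | None: expressly exempt |
| 5 | Monitoring not possible | None: acts as a fallback if no repeat can be obtained |

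Two of the five conflict.

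**2. Does the decision change, or only its timing?** Take a patient with a normal baseline, ALT 4× ULN, total bilirubin 3× ULN and a repeat ALT of 2.8× ULN.

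- Confirmation text: 4 ≥ 3 and 4 < 8, so a repeat is needed. 2.8 < 3, so the finding is not confirmed. No stop follows, and the confirmation-dependent evaluations and monitoring are not triggered.
- First Stopping Rule: 4 ≥ 3 and 3 > 2, so IMP stops. The fixed follow-up is at least 30 days; 30/7 = 4.3, so at least 4 weekly tests.

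The decision itself differs.

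**3. Which doses are at stake?** IMP is given only at weeks 0, 4 and 8 (Section 5.1), and laboratory tests are done at every visit (Table 2).

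- Week-4 dose: the last scheduled sample before that visit is the predose one at visit 2, so only that sample or an unscheduled test can bring this dose into play.
- Week-8 dose: this depends on the week-4 sample, the only scheduled on-treatment test with a later dose to influence.
- Number of week-8 injections: 300 with no drop-out, or 3 × 86 = 258 at the planned completer number (Section 9.1). Of these, 100 or 86 contain fremanezumab, because the 675-mg and placebo groups receive placebo then (Section 3.1).
- Time for a repeat, from the Table 2 windows: shortest (56 − 3) − (28 + 3) = 22 days, longest (56 + 3) − (28 − 3) = 34 days. A repeat will normally be back in time, so the dose is at stake mainly when the repeat falls below the confirmation limit.

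**4. How many patients?** The documents give no rate for the first two rules. The range below is an assumption.

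| Assumed rate | Of 300 patients | Of 100 in the 900-mg iv group |
|---|---|---|
| 0.1% | 0.3 | 0.1 |
| 1% | 3 | 1 |

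These counts cover any trigger at any time, so they are upper bounds. A changed dose also needs the trigger in the right sample and an unconfirmed repeat.

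**The case against.** The strongest reply is that the appendix can be read in sequence: confirm first, then apply the Stopping Rules. The repeat step collects bilirubin and symptoms, which those rules use. Section 7.4 also speaks of laboratory abnormalities confirmed by repeat testing before they lead to withdrawal. This reading is possible, but it is not written. It leaves the word *immediately* in rules 1 and 2 with no work to do, and rule 3 states its own repeat-testing condition where rules 1 and 2 state none. Section 7.4 concerns the recording of adverse events and sets no precedence.

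The opposite reading, that the Stopping Rules override, is not secure either. Rule 4 is on the list and still gets an express waiver of confirmation; rules 1 and 2 get none.

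A reader might infer that an unconfirmed patient is left without follow-up. The documents do not support that. Section 7.1.2 requires adverse events to be followed to resolution or another defined end, and Section 7.4 brings clinically significant laboratory results under it. ALT or AST ≥3× ULN is an event of special interest (Section 7.1.7), reported on the 24-hour serious-event route (Section 7.1.5.3.1). A repeat of 2.8× ULN still calls for the history, examination and alcohol advice that Appendix J requires from 2× ULN.

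A reader might also infer that leaving INR out of the repeat makes the INR limb of rule 1 unworkable. It does not: INR is in the laboratory panel (Appendix M) at every visit and can be judged on the first sample.

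Section 7.1.2 refers to a Safety Monitoring Plan that is not among these documents and may settle the matter. The protocol text that sites are sent to would still be inconsistent.

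**Conclusion.** The point stands: wrong as written, an internal contradiction in a safety rule, with low impact. Followed literally, the confirmation text would keep a patient with a possible Hy's law pattern on IMP because the repeat ALT fell just below 3× ULN, while the first Stopping Rule would stop IMP.

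The difference is confined to the stop itself and the fixed schedule of at least 30 days with at least weekly enzymes. The schedule can differ even after the last dose. At the assumed 0.1% to 1%, no more than 0.3 to 3 of 300 patients would meet rule 1 or 2, and far fewer would have a dose changed.

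It would be too strong to conclude that patients are left unprotected or that the efficacy result is threatened. The sponsor can request withdrawal, and the investigator must withdraw a patient for whom continuing is not in their best interest (Section 4.3, items 6 and 7). The primary endpoint covers weeks 0 to 4, before the week-8 dose, so it would rarely be touched. These safeguards rest on judgement in each case and do not say which written rule governs.

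**What to change.** Extend the exemption note in Appendix J by cross-reference, for example:

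> IMP is to be stopped without waiting for a confirmatory test when ALT or AST is ≥8× ULN, or when the first or second Stopping Rule below is met as written. The repeat test and the additional evaluations are still to be done.

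A cross-reference is better than restating the rules. It keeps both qualifiers in the second rule: the symptoms must clearly point to the liver and must not be attributed to another disease. Without them, nausea caused by a cluster attack could waive confirmation. Isolated elevations of 3× to <8× ULN remain confirm-first.

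The cost is one sentence, by amendment or clarification letter. It adds no visits and no new types of test, since Appendix J already asks for the repeat and for the additional evaluations after a stop. The downside is that a very few patients whose elevation would not have been confirmed stop IMP, as the Stopping Rules already direct.
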